## 3.5 Pharmacokinetic Assessment

PK samples for AP-SA02 will be collected prior to and post study drug.

The PK analysis will be described by a separate PK Analysis Plan and the PK Population will not be included in this SAP analyses. Calculation and analysis of PK parameters will be described and reported by the Sponsor separately.

## 3.6 Pharmacodynamic Assessment

Pharmacodynamic assessment will be conducted for ITT population, Per Protocol MITT population, Phage Persistence and Clearance population, and Phage-Sensitivity ITT population (if needed):

- Efficacy analysis performed using ITT population and Phase-Sensitivity ITT population (if needed) will be summarized by pooled treatment versus pooled placebo for Phase 1b and Phase 2a:
  - Phase 1b (uncomplicated SAB) vs Phase 1b placebo

- Phase 2a (complicated SAB) vs Phase 2a placebo.
- Efficacy analysis performed using Per Protocol MITT population will be summarized by pooled treatment versus pooled placebo for Phase 2a:
  - Phase 2a vs Phase 2a placebo.
- Efficacy analysis performed using Phage Persistence and Clearance population will be summarized by following:
  - Combination of Phase 1b (excluding cohort 1) and Phase 2a Persistence vs Combination of Phase 1b (excluding cohort 1) and Phase 2a Clearance vs Combination of Phase 1b placebo (excluding cohort 1) and Phase 2a placebo
  - Phase 2a Persistence vs Phase 2a Clearance vs Phase 2a placebo

Combination of Phase 1b placebo (excluding cohort 1) and Phase 2a placebo includes Phase 1b placebo (excluding cohort 1) and Phase 2a placebo in ITT population. Phase 2a placebo includes Phase 2a placebo in ITT population.

Phage Persistence and Phage Clearance Population and Phage-Sensitivity ITT population (if needed) will be reported by the Sponsor separately. Subject lists for Phage Persistence and Phage Clearance Population and Phage-Sensitivity ITT population (if needed) will be provided by Sponsor for analysis.

Time to initial resolution of SAB will be analyzed using the Kaplan-Meier method, and the resolution will be defined as “2 consecutive days with negative SA blood cultures” based on blood cultures tested by the local microbiology laboratories. Blood cultures collected at Day 1 prior to first dose of study drug will be considered for initial resolution of SAB.

If Day 12 blood culture is positive, the subject will not be considered have initial resolution of SAB although there may be 2 or more consecutive negative blood cultures before Day 12. If EOS or BAT blood culture is positive, the subject will be considered as initial resolution of SAB when there are 2 or more consecutive negative blood cultures before EOS or BAT, and the initial resolution date and time will be the first date and time with 2 consecutive negative blood cultures. The subjects who do not experience the resolution will be censored at the last collection date and time of blood culture.

- Time to initial resolution of SAB (days) = (Censoring date and time/first date and time of 2 consecutive days with negative SA blood culture – date and time of first dose of study drug) /3600/24

The Kaplan-Meier method will be used to estimate the 25%, median and 75% times. The hazard ratio, 95% confidence interval (CI) of hazard ratio, and p-value from Cox regression model will be provided to compare AP-SA02 and placebo. Cox regression will include treatment (AP-SA02 and placebo) as factor.

The Kaplan-Meier plot of time to initial resolution of SAB will be provided.

Time to resolution of any signs and/or symptoms of bacteremia present at Screening will be analyzed using the Kaplan-Meier method as other time-to-event endpoints.

- Time to resolution of signs/symptoms of bacteremia (days) = Censoring date/date of first resolution of any signs/symptoms of bacteremia - date of first dose of study drug + 1

The Kaplan-Meier method will be used to estimate the 25%, median and 75% times. The hazard ratio, 95% confidence interval (CI) of hazard ratio, and p-value from Cox regression model will be provided to compare AP-SA02 and placebo. Cox regression will include treatment (AP-SA02 and placebo) as factor.

The Kaplan-Meier plot of time to resolution of any signs and/or symptoms of bacteremia present at Screening will be provided.

The signs and symptoms of SAB will be determined programmatically based on the following:

- Documented temperature  $\geq 38.0^{\circ}\text{C}$  ( $100.4^{\circ}\text{F}$ ) or  $\leq 36.0^{\circ}\text{C}$  ( $96.8^{\circ}\text{F}$ ) measured orally,  $\geq 38.5^{\circ}\text{C}$  ( $101.3^{\circ}\text{F}$ ) or  $\leq 36.5^{\circ}\text{C}$  ( $97.7^{\circ}\text{F}$ ) measured tympanically, or  $\geq 39^{\circ}\text{C}$  ( $102.2^{\circ}\text{F}$ ) or  $\leq 37^{\circ}\text{C}$  ( $98.6^{\circ}\text{F}$ ) measured rectally;
- Heart rate  $>90$  beats per minute;
- Respiratory rate  $>20$  breaths per minute;
- White blood cell count  $\geq 12.0 \times 10^9$  cells/L or  $\leq 0.4 \times 10^9$  cells/L, or  $\geq 10\%$  immature neutrophils;
- Systolic blood pressure  $<90$  mmHg; and/or
- Pain associated with focal site of infection.

CRP and Interleukin-10 results will be summarized with descriptive statistics at baseline, each scheduled post-baseline visits. Changes from baseline for each scheduled post-baseline visit, the minimum, maximum, last post-baseline value. Both scheduled and unscheduled post-baseline values will be considered for the summaries. A paired t-test p-value will be used to compare the baseline value with each scheduled post-baseline values. An unpaired t-test p-value will be used for the change from baseline at each scheduled study day to compare AP-SA02 and placebo.

Changes from baseline will be plotted by AP-SA02 and placebo at each scheduled study day for each subject.

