4.1 Inclusion Criteria

Inclusion criteria for Phase 1b and 2a

Subjects who meet all of the following criteria will be eligible to participate in the study:

1. Is able and willing to provide written informed consent or have consent provided by an LAR;
2. Is a hospitalized male or female adult subject aged 18 years or older at time of consent;
3. Has SAB identified from at least 1 blood culture or from a rapid diagnostic test within 72 hours of randomization. Time of positive blood culture starts from when specimen is collected for blood culture;
4. Has a plan for source control within 3 days after randomization to be completed within 7 days of randomization if relevant (eg, abscess drainage, washout or debridement of infected material) or has source already controlled;
5. If an FCBP, the subject must agree to use a highly effective method of birth control (defined as those, alone or in combination, that result in a low failure rate [ie, less than 1% per year]) from Day 1 through 60 days following the last dose of study drug;

Note: FCBP must have a negative serum pregnancy test within 72 hours prior to randomization. An FCBP is any female, regardless of sexual orientation, who meets the following criteria: has not undergone a hysterectomy or bilateral oophorectomy, or has not been naturally postmenopausal for at least 12 consecutive months (ie, has had menses at any time in the preceding 12 consecutive months).

6. If a male subject, the subject must agree to use barrier contraception (ie, condoms) from Day 1 through 60 days following the last dose of study drug;

Additional inclusion criteria for Phase 2a only

7. Has at least 1 of the following signs/symptoms at or within 72 hours prior to randomization:
 - a. Documented temperature $\geq 38.0^{\circ}\text{C}$ (100.4°F) or $\leq 36.0^{\circ}\text{C}$ (96.8°F) measured orally, $\geq 38.5^{\circ}\text{C}$ (101.3°F) or $\leq 36.5^{\circ}\text{C}$ (97.7°F) measured tympanically, or $\geq 39^{\circ}\text{C}$ (102.2°F) or $\leq 37^{\circ}\text{C}$ (98.6°F) measured rectally;
 - b. Heart rate >90 beats per minute;
 - c. Respiratory rate >20 breaths per minute;
 - d. White blood cell count $\geq 12.0 \times 10^9$ cells/L or $\leq 0.4 \times 10^9$ cells/L, or $\geq 10\%$ immature neutrophils;
 - e. Systolic blood pressure <90 mmHg; and/or
 - f. Pain associated with focal site of infection.

8. Has at least 1 of the following:

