**Table 2. Time-to-event Endpoint**

Endpoint: time to reach a NEWS2 score <math>\leq 2</math> maintained for at least 24 hours or hospital discharge		
Situation	Date of event or censoring	Outcome
NEWS2 score $\leq 2$ maintained consecutive 2 days while hospitalized	Earlier date of these two consecutive 2 days	Event
Hospital discharge (i.e., Discharge to home, transferred to long term acute care – LTAC, transferred to long term care facility – LTCF) and no NEWS2 score $\leq 2$ maintained consecutive 2 days while hospitalized	Date of hospital discharge	Event
No occurrence of hospital discharge to home and no NEWS2 score $\leq 2$ maintained consecutive 2 days	Date of last visit	Censored

In [Table 2](#), the hospital discharge types include discharge to home, transferred to long term acute care – LTAC, and transferred to long term care facility – LTCF.

Proportion of subjects reaching a NEWS2 score  $\leq 2$  maintained for at least 24 hours or hospital discharge (whichever comes first) at Day 2, Day 3, Day 4, Day 5, Day 7, and TOC for study drug (Day 12) will be analyzed. The hospital discharge types include discharge home, transferred to long term acute care – LTAC, and transferred to long term care facility – LTCF. The responders will be subjects reaching a NEWS2 score  $\leq 2$  maintained for at least 24 hours or hospital discharge. Proportion of responders will be provided. Chi-square test p-value will be provided to compare AP-SA02 and placebo.

The proportion of subjects reaching a NEWS score  $\leq 2$  maintained for at least 24 hours or hospital discharge (whichever comes first) will be plotted by AP-SA02 and placebo at Day 2, Day 3, Day 4, Day 5, Day 7, and TOC for study drug (Day 12).

NEWS2 score while hospitalized will be summarized with descriptive statistics by study day and changes from baseline for each study day will be summarized. A paired t-test p-value will be used to compare the baseline value with each scheduled post-baseline values. An unpaired t-test p-value will be used for the change from baseline at each scheduled study day to compare AP-SA02 and placebo.

NEWS2 score while hospitalized and changes from baseline will be plotted by AP-SA02 and placebo at each scheduled study day for each subject.

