**Table 3. Microbiological Outcome**

Category	Criteria
Eradication	Blood cultures negative for SA for 2 consecutive days.
Presumed eradication	Follow-up blood cultures were not done (or were technically uninterpretable) and the subject has responded clinically, as defined in Table 2 of protocol .
Persistence	Follow-up blood cultures do not meet the criteria for eradication and are positive for SA either daily or every other day.
Presumed persistence	Follow-up blood cultures were not done (or were technically uninterpretable) and the subject has not responded clinically, as defined in Table 2 of protocol .
Recurrence	A positive blood culture for SAB at any time after documented eradication or presumed eradication.

In [Table 3](#), “the subject has responded clinically” indicates that the subject experiences clinical improvement or response per investigator’s assessment at EOT for study drug. Any 2 consecutive assessments with blood cultures negative for SA is assigned as Eradication programmatically, no matter if these 2 assessments are consecutive days or consecutive visits.

Time to first resolution of any signs/symptoms related to focal site of SA infection (e.g., joint pain; redness; swelling; weight-bearing, back pain; weight-bearing, skin redness; drainage) from randomization on Day 1 will be analyzed. If all signs/symptoms are absent, the subjects will be considered achieving the resolution of signs/symptoms related to focal site of SA infection. If any signs/symptoms are present during the study assessments, the subjects will be censored at the date of latest assessment of signs/symptoms assessments for focal site of SA infection.

Time-to-event (days) = Censoring date/date of first resolution assessment – date of first dose of study drug + 1

The Kaplan-Meier method will be used to estimate the 25%, median and 75% times. The hazard ratio, 95% confidence interval (CI) of hazard ratio, and p-value from Cox regression model will be provided to compare AP-SA02 and placebo. Cox regression will include treatment (AP-SA02 and placebo) as factor. All assessments from scheduled and unscheduled visits will be included in the time-to-event analysis.

The Kaplan-Meier plot of time to first resolution of any signs/symptoms related to focal site of SA infection will be provided.

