Late composite efficacy will be assessed programmatically based on the blood cultures tested by local microbiology laboratories per the definition in [section 2.3.2](#) at EOS. Proportion of subjects who experience late composite efficacy will be provided. Chi-square test p-value will be provided for the counts of subjects who experience late composite efficacy to compare AP-SA02 and placebo.

Microbiological failure or relapse will be assessed programmatically based on the blood cultures tested by local microbiology laboratories per the definition in section 2.3.2. Proportion of subjects who experience microbiological failure or relapse at TOC for study drug (Day 12), TOC for BAT (7 days [ $\pm 1$  day] after the end of BAT) and EOS (28 days after the end of BAT) will be provided.

If subjects have microbiological failure or relapse at TOC for study drug (Day 12) and negative blood cultures after Day 12, then subjects will not be included as microbiological failure or relapse at TOC for BAT (7 days [ $\pm 1$  day] after the end of BAT) or EOS (28 days after the end of BAT). If subjects have microbiological failure or relapse at TOC for BAT (7 days [ $\pm 1$  day] after the end of BAT) and negative blood cultures after TOC for BAT, then subjects will not be included as microbiological failure or relapse at EOS (28 days after the end of BAT). Chi-square test p-value will be provided for the counts of subjects who experience microbiological failure or relapse to compare AP-SA02 and placebo.

Time to death will be analyzed. Subject alive will be censored at the last date to be known alive.

$$\text{Time to death (days)} = \text{Censoring date/death date} - \text{date of first dose of study drug} + 1$$

The Kaplan-Meier method will be used to estimate the 25%, median and 75% times. The hazard ratio, 95% confidence interval (CI) of hazard ratio, and p-value from Cox regression model will be provided to compare AP-SA02 and placebo. Cox regression will include treatment (AP-SA02 and placebo) as factor.

Time to hospital discharge (and time to hospital discharge readiness) will analyzed. The subjects who will be in the hospital during the study will be censored at the date of last visit.

- Time to hospital discharge (days) = Censoring date/first hospital discharge date – date of first dose of study drug + 1
- Time to hospital discharge readiness (days) = Censoring date/first hospital discharge readiness date – date of first dose of study drug + 1

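### The time-to-event rules admit subjects already culture-negative or sign-free at entry (with negative times possible for SAB resolution) and leave deaths before recovery to be censored by default

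*SAP*

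**What the plan says.** **SAB resolution (SAP 3.6).** Resolution is two consecutive days of negative cultures, and "Blood cultures collected at Day 1 prior to first dose of study drug will be considered for initial resolution of SAB". The event is placed at the "first date and time of 2 consecutive days with negative SA blood culture", from which the date and time of first dose is subtracted. Nothing is added and there is no floor at zero. A positive Day 12 culture cancels the event. Unresolved subjects are censored at their last culture.

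**NEWS2 (SAP 3.4.1, Table 2).** The event date is the "Earlier date of these two consecutive 2 days" with a score of 2 or less, or the discharge date. Time is the event date minus the first-dose date, plus 1. Everyone else is censored at the last visit.

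**Focal signs (SAP 3.4.1).** "If all signs/symptoms are absent, the subjects will be considered achieving the resolution of signs/symptoms related to focal site of SA infection". No baseline sign is expressly required. The next sentence censors, at the latest assessment, any subject with a sign present during the study assessments.

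**Discharge (SAP 3.4.1).** "The subjects who will be in the hospital during the study will be censored at the date of last visit".

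None of these rules mentions death. Each endpoint gets Kaplan-Meier quartiles and a Cox model with treatment as the only factor, reported with a hazard ratio (HR), confidence interval and p-value. Time to death is a separate endpoint.

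**The concern.** A time-to-resolution analysis should start with subjects who have something to resolve, and its clock should not run backwards. Here a subject who cleared the blood on antibiotics alone can be an event before time zero. The SAP does not say whether such a time is dropped, set to zero or kept, so two programmers could produce different results. If kept, the event is one that study drug had little or no chance to influence. The NEWS2 and focal-sign rules raise the same issue in milder form.

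Separately, a subject who dies in hospital can no longer recover or be discharged. Kaplan-Meier treats a censored subject as still able to do so, which affects the curves and quartiles that the SAP will report.

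**Working it through.** **1. The plan's own figure.** The documents give no design figure for any time-to-event endpoint. The only one is at least 80% power for Day 12 clinical response (38 subjects, 80% against 30%, one-sided 0.05, Fisher's exact test). Exact enumeration gives 87.8% at 25:13 and 86.3% at 26:12, so it reproduces. This point does not rest on it.

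**2. Can a subject be culture-negative at dosing and still be analysed?** Yes. Baseline SAB needs one positive culture within 72 hours before first dose (SAP 3.1.2). Up to 72 hours of effective prior antibiotic is allowed (Protocol 4.2, exclusion 3). The Day 1 culture is drawn close to dosing, or replaced by one already sent that day (Protocol 7.7).

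**3. Date arithmetic for SAB resolution.** Take a pre-dose Day 1 negative followed by a Day 2 negative.
- Dated to the first culture, drawn 30 minutes before dosing: -30 × 60 / 86,400 = -0.02 day. Drawn 12 hours before: -0.5 day.
- Dated to the second, post-dose culture: the time is positive.

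The SAP also says that "the initial resolution date and time will be the first date and time with 2 consecutive negative blood cultures". The first of the pair is the more natural reading, but it is not spelled out.

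**4. NEWS2 and focal signs.** Inclusion 7 (Protocol 4.1) reads "Has at least 1 of the following signs/symptoms at or within 72 hours prior to randomization". It can be met by focal pain or white cell count (neither is a NEWS2 component), heart rate 91 to 110 (1 point) or respiratory rate 21 to 24 (2 points). No criterion requires NEWS2 above 2. With scores of 2 or less on Days 1 and 2, the time is 0 + 1 = 1 day. A subject with no focal sign on Day 1 also has time 1. Neither is negative.

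**5. How many could be affected?** The documents give no rate. If 20% to 60% of 38 subjects were culture-negative before dosing (assumption), 38 × 0.2 = 7.6 and 38 × 0.6 = 22.8, or about 8 to 23. This is a ceiling: each must also have a second consecutive negative and no positive Day 12 culture.

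**6. Effect on the HR.** Large simulated 2:1 trials (60,000 subjects), placebo resolution hazard 0.25 per day (assumption), follow-up to Day 12, pre-dose events placed at time 0:

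| Pre-dose events | True HR 1.0 | True HR 1.5 | True HR 2.0 |
|---|---|---|---|
| 0% | 1.00 | 1.49 | 2.02 |
| 10% | 0.98 | 1.44 | 1.87 |
| 20% | 0.98 | 1.39 | 1.73 |
| 30% | 0.98 | 1.32 | 1.61 |
| 50% | 1.01 | 1.24 | 1.41 |

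At 38 subjects, true HR 2.0 and 30% pre-dose events, the chance of two-sided p<0.05 is about 25% with those subjects included and 31% with them excluded. It is 46% if there are none. With no true effect it is about 6% either way.

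**7. Effect of censoring deaths.** Assume a recovery hazard λ = 0.15 per day, 11 days of follow-up, and a death hazard μ chosen to give the stated share of deaths.
- One minus Kaplan-Meier: 1 - exp(-0.15 × 11) = 80.8%, whatever the death rate.
- True cumulative incidence: λ/(λ+μ) × [1 - exp(-(λ+μ) × 11)].

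| Deaths | μ | True recovered | Overstatement |
|---|---|---|---|
| 5% | 0.0096 | 77.7% | 3.1 points |
| 10% | 0.0201 | 74.6% | 6.2 points |
| 20% | 0.0440 | 68.2% | 12.6 points |

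With a true recovery HR of 1.5 and equal death hazards, the Cox HR returns 1.5. If the drug doubled the death hazard and did nothing to recovery, the Cox HR would be 1.0, while the subdistribution HR would be 0.94, 0.90 and 0.82.

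**The case against.** A reader might infer that these hazard ratios do not measure drug effect at all. The documents do not support that. Phase 2a is randomized, so pre-dose events balance between arms in expectation: they dilute the HR but leave it near 1 when there is no effect. With deaths censored, the Cox HR is a valid cause-specific HR. A reader might also refit the discharge model with deaths held as never discharged, get a different HR, and take the gap as bias. Those are two estimands, and the gap does not show an error.

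Other objections stand in part:
- Negative times are confined to SAB resolution and depend on dating the event to the first negative. Only the Day 1 pre-dose culture is named, so the second negative normally follows dosing; such a subject has not fully met the resolution definition before the drug starts.
- The Day 1 NEWS2 score is not stated to be pre-dose.
- Resolution of a focal sign ordinarily implies that the sign was present, so that item may need only clearer wording.
- Censoring of deaths follows from silence and catch-all rows, with no express rule. Death is counted elsewhere: in time to death, as non-response in Protocol Table 2, and in late composite efficacy.
- The SAP plans no formal testing, and the sample size does not rest on these endpoints.

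The last item lowers the stakes without removing them, because HRs, intervals, p-values and quartiles will still be reported. Randomization also gives no protection in the Phage Persistence versus Clearance comparisons (SAP 3.4 and 3.6). Those groups are formed by phage recovery 3 hours after the first dose, so a difference in pre-dose clearance between them could confound the result.

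**Conclusion.** The rules are wrong as written and should be fixed before database lock, but they do not void the randomized comparison. The SAB resolution endpoint cannot be programmed unambiguously and, on the natural reading, yields negative times. NEWS2 and focal-sign events can fall on Day 1 in subjects with nothing to resolve. Read literally, the focal-sign censoring sentence also censors subjects who later clear.

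The expected consequence between randomized arms is an HR pulled toward 1, with no false effect created. Between the Persistence and Clearance groups, confounding is possible. Kaplan-Meier recovery would be overstated by about 3 to 13 points for deaths of 5% to 20%, and the recovery HR would not reflect an effect on death. Time to death is unaffected. All sizes rest on assumed clearance, recovery and death rates, since the documents give none.

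**What to change.** 1. **SAB resolution (SAP 3.6).** State which negative culture dates the event. Make the main analysis subjects whose last pre-dose culture is positive, using post-dose cultures only. Tabulate those already negative before dosing. Keep the full set as a sensitivity analysis with times floored at 0.
2. **Focal signs (SAP 3.4.1).** Restrict to subjects with at least one focal sign at baseline, and censor only those who never clear.
3. **NEWS2 (SAP 3.4.1).** Restrict to baseline NEWS2 above 2, or stratify by 2 or less against above 2. Say which score is baseline: Appendix A schedules NEWS2 from Day 1 and does not say that the Day 1 score precedes dosing.
4. **Deaths.** For NEWS2, discharge and SAB resolution, add an explicit rule: report Aalen-Johansen cumulative incidence with death as a competing event, and label the Cox HR as cause-specific.

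The cost is SAP wording and programming on data the study already collects. The main downside is smaller restricted sets: at the ceiling in step 5, 38 - 7.6 = 30.4 down to 38 - 22.8 = 15.2, or about 30 to 15 subjects. That is why the full-set analysis should be kept alongside.
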